Attachment I list of key staff and relevant departments and suppliers

Protocol Trial ID: NN7008-4304 UTN:U1111-1179-5950 EudraCT no.:2017-002281-46

CONFIDENTIAL

Date: Version: Status: Page:

13 June 2017 | Novo Nordisk 2.0 Final 6 of 81

Table of figures

		Page
Figure 12–1	Reporting of AEs	53
Table of	tables	
		Page
Table 1–1	Trial products	8
Table 2–1	Visit flow chart	10
Table 5–1	Guide for trial product dosing in bleeding episodes ¹	18
Table 8–1	Minimum requirements for washout periods	25
Table 8–2	Definition of stop of a bleeding episode	31
Table 8–3	Definition of haemostatic response	31
Table 8–4	Definition of bleeding episode severity	32
Table 8–5	Definition of bleeding episode categorisation	32
Table 8–6	Definition of surgery type	36
Table 8–7	Overview of samples for future research (biospecimen)	40
Table 9–1	Trial products	43
Table 9–2	Storage conditions	44

Protocol Date: 13 June 2017 Novo Nordisk

 Trial ID: NN7008-4304
 Version:
 2.0

 UTN:U1111-1179-5950
 Status:
 Final

 EudraCT no.:2017-002281-46
 Page:
 7 of 81

List of abbreviations

AE adverse event

AR adverse drug reaction

BU Bethesda unit
BW body weight
CL clearance

CRA clinical research associate

CRF case report form

CVAD central venous access device

DFU directions for use
DUN dispensing unit number
eCRF electronic case report form

ED exposure day

EMA European Medicines Agency

FVIII Factor VIII

GCP Good Clinical Practice
HLA human leucocyte antigen

ICH International Conference on Harmonisation

IEC independent ethics committee IRB Institutional Review Board

IU International units

i.v. intravenous

IWRS interactive web response system

Kg Kilogram

LAR legally acceptable representative

LPLV last patient last visit

mL millilitres
PK pharmacokinetic

PTP previously treated patients
pdFVIII plasma-derived factor VIII
rFVIII recombinant factor VIII
SAE serious adverse event
SAR Serious adverse reaction
SIF safety information form

SUSAR suspected unexpected serious adverse reaction

TMM trial materials manual

WFH World Federation of Haemophilia

UTN universal trial number

13 June 2017 | Novo Nordisk Protocol Date: Trial ID: NN7008-4304 Version: CONFIDENTIAL UTN:U1111-1179-5950 Status: Final EudraCT no.:2017-002281-46 8 of 81

Page:

1 Summary

Objective(s) and endpoint(s):

Primary objective:

To assess safety of turoctocog alfa during treatment and prophylaxis of bleeding episodes in previously treated patients with moderate or severe Haemophilia A in India

Secondary objective:

To assess efficacy outcomes with turoctocog alfa during treatment and prophylaxis of bleeding episodes in previously treated patients with moderate or severe Haemophilia A in India

Primary endpoint:

• Occurrence of confirmed FVIII inhibitor development (≥ 0.6 BU) during 8 weeks of treatment

Secondary endpoints:

- Frequency of adverse drug reactions (AR) and serious adverse reactions (SAR) reported until follow-up, 12 weeks after first treatment
- Successful haemostatic effect of turoctocog alfa in the treatment of bleeding episodes during 8 weeks of treatment
- Total annualised consumption of turoctocog alfa measured during the 8 weeks of treatment
- Frequency of allergic or infusion reactions related to the trial product reported until follow-up, 12 weeks after first treatment

Trial design:

This trial is a single-country, multicentre, open-label and non-randomised trial with turoctocog alfa treatment and prophylaxis of bleeding episodes in previously treated patients with moderate or severe Haemophilia A for 8 weeks corresponding to at least 20 EDs.

Trial population:

60 previously treated patients (PTPs, ≥150 EDs with any FVIII containing product), 12 years or older, with congenital moderate or severe haemophilia A (FVIII $\leq 5\%$) with no history of inhibitors of FVIII, will be enrolled to allow for at least 50 patients to complete the trial.

Assessments:

Presence of FVIII inhibitors will be tested at visit 1 (screening) and visit 4 (end of trial)

Trial products:

Table 1-1 **Trial products**

The following trial products will be provided by Novo Nordisk:

Protocol Trial ID: NN7008-4304 UTN:U1111-1179-5950 EudraCT no.:2017-002281-46

CONFIDENTIAL

Date: Version: Status: Page:

13 June 2017 | Novo Nordisk 2.0 Final 9 of 81

Trial product	Strength	Dosage form	Route of administration
Turoctocog alfa	2000 IU/vial	Powder for solution for injection	Intravenous injection
Sodium Chloride	0.9%	Solvent for solution for injection	Intravenous injection

Date: Version: Status: Page:

13 June 2017 | Novo Nordisk 2.0 Final 10 of 81

Flow chart 2

Table 2–1 Visit flow chart

Trial Periods	Information visit	Screening	Baseline	Treatment	End of trial	Follow-up	Unscheduled Visit
Visit number	0	1	2	3	4	5	
Timing of visit Weeks from baseline	-4	-3	0	4	8	12 ^a	
Visit window Days	0	±2	±7	±3	±3	±3	
SUBJECT RELATED INFO/ASSESSMENTS							
In/exclusion criteria		X	X				
Withdrawal criteria			X	X			X
Criteria for premature discontinuation of trial product			X	X			X
Concomitant illness		X					
Concomitant medication		X	X	X	X		X
Haemophilia treatment and bleed history		X					
Medical history		X					
Details of Haemophilia		X					
Informed consent	X	X					
Informed assent	X^{b}	X^{b}					
Genotyping consent, optional		X ^c					
Biospecimen consent		X^{b}					
Demography		X					
Body measurements		X					
Height		X					
Body weight		X	X	X			Xb
EFFICACY							
Bleeding episodes			X^d	X ^d	X ^d		

Protocol Trial ID: NN7008-4304 UTN:U1111-1179-5950 EudraCT no.:2017-002281-46

CONFIDENTIAL

Date: Version: Status: Page:

3 June 2017 2.0 Final 11 of 81

13 June 2017 | Novo Nordisk

						1
Information visit	Screening	Baseline	Treatment	End of trial	Follow-up	Unscheduled Visit
0		_	2	4	-	
			_		_	
0	±2	±7	±3	±3	±3	
	X				X	X
		X	X			X
	X					
		Xe	Xe			Xe
		Xe	Xe			Xe
		Xf	Xf	Xf		X^{f}
	X			X		
	X^{g}					
	X			X		
	X^h					
	X^h					
	X ^c					
	Xi			Xi		X ^b
		X^{j}				X^{j}
		X	X			
	X	X	X	X		X ^b
		X	X	X		
			X	X		
		X	X^{b}			X ^b
	X					
		X	X	X		
	Information visit	0 1 -4 -3 0 ±2 X X X X X X X X X X X X X	0	0	0	0 1 2 3 4 5 -4 -3 0 4 8 12 ^a 0 ±2 ±7 ±3 ±3 ±3 X X X X X X X X X X X X X X X X X X X X X X X X X X X X X X X X X X X X X X X X X X X X X X X X X X X X X X X X X X X X X X X X X X X X X X X X X X X X X X X X X X X X X X X X X X X X X X X X X X X X X X X X X X X X X X X X X X X X X X X X X X X X X X X X X X X X X X X X X X X X X X X X X X X X X X X X X X X X X X X X X X X X X X X X X X X X X X X X X X X X X X X X X X X X X X X X X X X X X X X X X X X X X X X X X X X X X X X X X X X X X X X X X X X X X X X X X

Protocol		Date:	13 June 2017	Novo Nordisk
Trial ID: NN7008-4304	CONFIDENTIAL	Version:	2.0	
UTN:U1111-1179-5950	CONFIDENTIAL	Status:	Final	
EudraCT no.:2017-002281-46		Page:	12 of 81	

- X^a If patient has withdrawn the follow-up-visit must be performed 4 weeks after end of trial visit
- X^b If applicable
- X° Genotype consent is not mandatory at visit 1, but has to be collected before genotype is sampled, see section 8.5.3.1
- X^d Bleeding episodes and dosing information are recorded in the diary
- X^e If hypersensitivity reaction or technical complaints are identified, please ensure to complete the relevant form, see sections 12.1.5 and 12.1.6
- X^f If patient had any surgical interventions (minor surgery), please ensure to complete the surgery form, see section 8.4.5
- X^g Baseline FVIII level, a washout period of 72 hours since last dosing of any FVIII concentrate is required before FVIII activity test, see section 8.5.2.3
- X^h Not mandatory at visit 1 if the patient previously has been tested within 6 month and it is documented in the medical journal
- X^{i} A washout period of 48 hours since last dosing of any FVIII concentrate is required before inhibitor testing
- X^j Injection of trial product at site

Protocol Trial ID: NN7008-4304 UTN:U1111-1179-5950 EudraCT no.:2017-002281-46

CONFIDENTIAL

Date: Version: Status: Page:

13 June 2017 | Novo Nordisk 2.0 Final 13 of 81

3 Background information and rationale for the trial

The trial will be conducted in compliance with this protocol, ICH GCP 1 and applicable regulatory requirements, and in accordance with the Declaration of Helsinki.²

In this document, the term investigator refers to the individual responsible for the overall conduct of the clinical trial at a trial site.

3.1 **Background information**

3.1.1 Epidemiology of Haemophilia A in the Indian population

Haemophilia A is an X-linked recessive disorder that is characterised by bleeding episodes. It results from the deficiency of factor VIII (FVIII). The severity of bleeding in Haemophilia A is generally correlated to FVIII level in the plasma. Haemophilia A is considered severe when plasma FVIII level <1%, moderate when plasma FVIII level is 1-5% and mild when plasma FVIII level is 5 - 40%. The mainstay of management of Haemophilia A is replacement of deficient FVIII. Main goals of therapy include not only treating bleeding episodes but also help patients lead a normal life with little compromise on quality of life (QoL) due to haemophilia. This is possible when clotting factors are administered for prophylactic use on a regular basis (to prevent the occurrence of a bleeding episode) instead of on-demand treatment (i.e. administered after each bleeding episode).³

The estimated number of haemophilia patients in India is over 70 000. ⁴ However less than a quarter of these patients are diagnosed and registered in India. The registered number of haemophilia patients in India is 17,470 which include 14,450 patients with Haemophilia A and 2281 patients with Haemophilia B. It is reported that among 14,450 patients, 30% belong to \leq 18 years of age and 33% belong to age group of 19 – 44 years. The main modality of management of haemophilia in India is on-demand regimen (i.e. administration of clotting factor after each bleeding episode). Patients visit their respective treatment centres for management of each individual bleeding episode. Less than 1% of Haemophilia A patients under age of 18 years receives prophylactic replacement in selected centres.²

3.1.2 Current standard of care

Among FVIII concentrates used in India in 2014, 98% consumption was plasma derived FVIII (pd-FVIII) and the remaining 2% was recombinant FVIII (rFVIII).⁵ This partly explains the inadequate supply and delay in supply of FVIII as pd-FVIII alone is not able to meet the patients' requirements as elsewhere in the world. Hence a significant proportion of Haemophilia A patients in India are still treated with blood or blood derived products, namely fresh frozen plasma and cryoprecipitate. The prevalence of HIV, Hepatitis B and Hepatitis C burden among patients with haemophilia due to use of blood products is approximately 1 %, 6 % and 30 % respectively. \(\frac{7}{8}\)

Protocol		Date:	13 June 2017	Novo Nordisk
Trial ID: NN7008-4304	CONFIDENTIAL	Version:	2.0	
UTN:U1111-1179-5950	CONFIDENTIAL	Status:	Final	
EudraCT no.:2017-002281-46		Page:	14 of 81	

The risk of infections in patients with Haemophilia A due to prions and small non-enveloped viruses like parvovirus B19 exists as these are neither removed nor inactivated in any of the currently available pd-FVIII in India. 5, 9, 10 The currently available first generation rFVIII uses albumin and other human/animal serum or proteins in various stages of production process which lowers their final purity. 5, 9 Concentrates of lower purity may give rise to allergic reactions. In addition it does not undergo any standard recommended purification technique namely solvent detergent method or nanofiltration as per World Federation of Haemophilia (WFH). Hence availability of recombinant FVIII concentrates is considered as an unmet need for management of patients of Haemophilia A in India.

3.1.3 Turoctocog alfa

Turoctocog alfa (NovoEight®), a third generation recombinant human coagulation factor VIII intended for prophylaxis and treatment of bleeding episodes in haemophilia A patients, was recently approved in India with a waiver for conducting a phase III clinical trial in Indian patients.

11

Turoctocog alfa is a recombinant factor VIII (rFVIII) with a truncated B-domain made from the sequence coding for 10 amino acids from the N-terminus and 11 amino acids from the C-terminus of the naturally occurring B-domain. The truncated B-domain was selected to achieve a well-defined product when produced by recombinant DNA technology in Chinese hamster ovary (CHO) cells. When turoctocog alfa is activated by thrombin, the truncated B-domain is cleaved, leaving an active FVIII molecule that is similar to endogenous FVIII in its activated form. It is a third generation factor VIII product prepared without the addition of any human or animal derived protein in the cell culture process, purification or final formulation. Turoctocog alfa is isolated from the culture media using an optimized five-step purification process: i) detergent inactivation and concentration; ii) immunoaffinity chromatography using a recombinant monoclonal antibody; iii) anion exchange chromatography; iv) nanofiltration with a 20 nm pore size filter; and v) a final gel filtration (size exclusion chromatography) step. Inactivation of enveloped viruses like HIV, HBV and HCV is ensured by detergent treatment (included in the initial purification step) and removal of prions and non-enveloped viruses like Parvovirus B19 is ensured by a 20-nm filtration step prior to the size exclusion step. ^{12, 13}

The First Human Dose and PK trial (NN7008-3522) results from 23 patients showed mean PK profiles of turoctocog alfa comparable to Advate® within the defined limits of comparability. In guardian™ 1 phase III trial, 150 previously treated (≥150EDs with other FVIII) adolescents/adults (≥12 year) with severe haemophilia A (and no history of inhibitors) received turoctocog alfa for 75 EDs. ¹³ In guardian™ 3 phase III trial 63 previously treated (≥ 50EDs with other FVIII) children (<12 year) with severe haemophilia A (and no history of inhibitors) received turoctocog alfa for 50 EDs, 188 of these patients continued into guardian™ 2 extension trial. ¹⁴ In the three trials, patients have received prophylaxis with turoctocog alfa three times weekly or every second day, or for treatment of breakthrough bleeding episodes. No safety concerns have arisen in any of the phase III trials, and no patients have developed confirmed inhibitors. ¹⁵, ¹⁶ Efficacy in bleeding prevention was

Protocol Trial ID: NN7008-4304 UTN:U1111-1179-5950 FudarCT ps. 2017, 202281 46	CONFIDENTIAL	Date: Version: Status:	13 June 2017 2.0 Final	Novo Nordisk
EudraCT no.:2017-002281-46		Page:	15 of 81	

demonstrated by a bleeding frequency within the range expected during prophylaxis treatment in haemophilia A (mean annualised bleeding rate of 6.5 bleeds/year in guardianTM 1 trial and 2.4 bleeds/year in guardianTM2 trial). Breakthrough bleeding episodes during prophylaxis were treated with turoctocog alfa and using a predefined four-point scale (Excellent, Good, Moderate or None), the haemostatic effect of turoctocog alfa was rated as excellent or good in 81 % of all bleeding episodes in guardianTM 1 trial and 91 % of all bleeding episodes in guardianTM 2 trial. For more information on safety and efficacy please refer to the Investigators brochure. ¹⁷

For an assessment of benefits and risks of the trial, see Section 18.1.

3.2 Rationale for the trial

This trial is a post-approval commitment. Novo Nordisk has been mandated by the Indian Health Authorities to conduct a phase 4 study with at least 50 patients with Haemophilia A. This trial will provide documentation on the safety and efficacy of turoctocog alfa in patients in India as no study has previously been conducted with turoctocog alfa in India. Novo Nordisk A/S has been required to provide NovoEight® for the participants and to include mandatory inhibitor tests. Therefore this commitment must be done as an interventional trial.

Inhibitor development in previously treated Haemophilia A patients have been shown to be an extremely rare event, with a frequency rate of 1-3 per 1000 patient years 18. It is thought to occur at random, without a clear association with a precipitating event such as switching to a new FVIII product 19. No difference between inhibitor incidence in PTPs treated with pdFVIII and rFVIII has been demonstrated in a large prospective registry based study 20.

 Protocol
 Date:

 Trial ID: NN7008-4304
 Version:

 UTN:U1111-1179-5950
 Status:

 EudraCT no.:2017-002281-46
 Page:

te: 13 June 2017 | **Novo Nordisk** rsion: 2.0 | ttus: Final ge: 16 of 81 |

4 Objective(s) and endpoint(s)

4.1 Objective(s)

Primary objective:

• To assess safety of turoctocog alfa during treatment and prophylaxis of bleeding episodes in previously treated patients with moderate or severe Haemophilia A in India

Secondary objectives:

• To assess efficacy outcomes with turoctocog alfa during treatment and prophylaxis of bleeding episodes in previously treated patients with moderate or severe Haemophilia A in India

4.2 Endpoint(s)

4.2.1 Primary endpoint

• Occurrence of confirmed FVIII inhibitor development (≥ 0.6 BU) during 8 weeks of treatment

4.2.2 Secondary endpoints

- Frequency of adverse drug reactions (AR) and serious adverse reactions (SAR) reported until follow-up, 12 weeks after first treatment
- Successful haemostatic effect of turoctocog alfa in the treatment of bleeding episodes during 8 weeks of treatment
- Total annualised consumption of turoctocog alfa measured during the 8 weeks of treatment
- Frequency of allergic or infusion reactions related to the trial product reported until follow-up, 12 weeks after first treatment

 Protocol
 Date:
 13 June 2017
 Novo Nordisk

 Trial ID: NN7008-4304
 Version:
 2.0
 2.0

 UTN:U1111-1179-5950
 Status:
 Final

Page:

17 of 81

5 Trial design

EudraCT no.:2017-002281-46

5.1 Type of trial

This is a single-country, multi-centre, open-label and non-randomised trial with a single treatment arm. 60 PTPs (≥150 EDs with any FVIII containing product) with moderate or severe haemophilia A will receive a prophylactic regimen with turoctocog alfa for a period of 8 weeks, which corresponds to at least 20 EDs on standard prophylaxis.

5.2 Rationale for trial design

This is a non-randomised trial and the design is common for trials with FVIII products in haemophilia A patients. In this trial, previously treated moderate or severe haemophilia A patients will receive routine prophylaxis treatment and treatment of bleeding episodes. This design is similar to the pivotal NN7008-3543 (guardianTM1) trial design and it is deemed adequate to fulfil the post-approval commitment requirements form the Indian Health Authority. The timeframe of 8 weeks (corresponding to \geq 20EDs on standard prophylactic treatment) provides an opportunity to detect an inhibitory response after initiation of treatment with turoctocog alfa in previously treated patients.

5.3 Treatment of patients

Patients will receive standard prophylaxis treatment and treatment of bleeding episodes, according to label. Trial product will be administered as intravenous injections (i.v.) at home by the patient or parent/LAR, at the trial site or in exceptional cases in another clinic/hospital. To be able to train patients on home treatment of turoctocog alfa at least the first treatment should be at the trial site.

Dosing for prophylaxis should be according to the approved prescribing information. The frequency of dosing can be either every second day or 3 times weekly, at a dose in the range 20-50 IU/kg. The individual regimen is chosen by the investigator, taking into account the patient's wishes, clinical status and readiness to comply with frequent dosing. The starting dose should be defined by the investigator within the recommended range based on clinical status. Dose adjustments can be made during the treatment period of 8 weeks within this range based on the patient's clinical status (bleeding frequency) at a visit.

Bleeding episodes will be treated with one or more turoctocog alfa i.v. bolus injections. The individual dose is determined by the investigator, using the recommendations in the World Federation of Haemophilia (WFH) guidelines³ and according to approved prescribing information.

Dose (IU) = weight (kg) x desired factor level (IU/dl) x 0.5

Example: $50 \text{kg} \times 40 \text{IU/dl} \times 0.5 = 1000 \text{ IU}$ of turoctocog alfa

In case of bleeding events, Table 5–1 as well as the WFH guideline_may be used to guide dosing. FVIII activity should not fall below the lower range for the given plasma activity level (in % of

Protocol		Date:	13 June 2017	Novo Nordisk
Trial ID: NN7008-4304	CONFIDENTIAL	Version:	2.0	
UTN:U1111-1179-5950	CONFIDENTIAL	Status:	Final	

Page:

18 of 81

normal or IU/dl) until the bleeding episode is resolved. As the guidelines are recommendations, non-compliance with them will not require protocol deviations. The highest dose per injection mentioned in this protocol should though not be exceeded.

Table 5–1 Guide for trial product dosing in bleeding episodes¹

EudraCT no.:2017-002281-46

Degree of haemorrhage	FVIII level required (%) (IU/dl)	Frequency of doses (hours)/ Duration of therapy (days)
Early haemarthrosis, muscle bleeding or oral bleeding	20-40	Repeat every 12 to 24 hours until the bleeding episode as indicated by pain is resolved or healing achieved
More extensive haemarthrosis, muscle bleeding or haematoma	30-60	Repeat injection every 12 to 24 hours for 3-4 days or more until pain and acute disability are resolved
Life-threatening haemorrhages	60-100	Repeat injection every 8 to 24 hours until threat is resolved

X¹ NovoEight® approved summary of turoctocog alfa characteristics

This formula may be used to calculate resulting factor levels:

IU/dl (or % of normal) = [Total Dose (IU)/BW (kg)] x 2 [IU/dl]/[IU/kg] Example: 2000 IU x ([2 IU/dl]/[IU/kg]) / 70 kg = 57 IU/dl

A dose of 2000 IU administered to a 70 kg patient should result in a post-injection FVIII level increase of 57 IU/dl, or 57%.

Bleeding treatment should start as soon as a bleeding episode is identified. The investigator should in advance provide the patient the doses needed to treat the bleed episode of different severities.

In case the patient suspects the bleed is severe it must be reported to the trial site if possible immediately or within 24 hours. See Table 8–4 for a definition of severe bleeding episodes. Furthermore, if there is no haemostatic improvement within 24 hours of the first trial product injection, the patient or parent/caregiver should immediately contact the investigator for advice. The investigator must always be contacted in case of bleeds that require treatment in a hospital setting and should be consulted for determination of dose and treatment duration if possible.

Recording into the diary should be made preferably within 24 hours from onset of the bleeding episode to ensure as correct information as possible. Any dose used for treatment of an active bleeding episode must be recorded as a treatment of a bleeding episode. When symptoms of active bleeding episode have stopped (e.g. pain is reduced and no increase in swelling/swelling diminishes), the patient or parent/caregiver can resume the prophylactic treatment. The timing of the next dose should be according to the prophylaxis dosing schedule.

Protocol		Date:	13 June 2017	Novo Nordisk
Trial ID: NN7008-4304	CONFIDENTIAL	Version:	2.0	
UTN:U1111-1179-5950		Status:	Final	
EudraCT no.:2017-002281-46		Page:	19 of 81	

For treatment in case of a minor surgical procedure, doses 30-60 IU/kg should be used. Treatment should be repeated every 24 hours as needed.

If the procedure takes place at another location than at the trial site (e.g. surgery site or dental practice), the surgeon/dentist must be informed that the patient is participating in the trial, and the investigator should give instructions in advance about the dosing and handling of the trial product.

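### Does the minor-surgery range of 30-60 IU/kg leave the per-injection dose cap in section 5.3 undefined?

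*Combined protocol and SAP*

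**What the plan says.** All the dosing text is in section 5.3 of the protocol.

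- **Prophylaxis** is given "every second day or 3 times weekly, at a dose in the range 20-50 IU/kg".
- **Bleeds** are treated with a dose the investigator sets from the WFH guideline and the approved prescribing information, with the conversion "Dose (IU) = weight (kg) x desired factor level (IU/dl) x 0.5". Table 5-1 gives target factor levels for three degrees of haemorrhage, the highest being 60-100 IU/dl with "Repeat injection every 8 to 24 hours until threat is resolved". For treatment outside the clinic, "The investigator should in advance provide the patient the doses needed to treat the bleed episode of different severities".
- **Status of the guidance**: "As the guidelines are recommendations, non-compliance with them will not require protocol deviations". The next sentence is the ceiling: "The highest dose per injection mentioned in this protocol should though not be exceeded".
- **Minor surgery**: "For treatment in case of a minor surgical procedure, doses 30-60 IU/kg should be used", and "Treatment should be repeated every 24 hours as needed". Table 5-1 has no surgery row.

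Section 5.5 attributes the trial's dose ranges and regimens, in general terms, to the approved prescribing information.

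**The concern.** The ceiling points to a maximum elsewhere in the protocol without giving its value, its unit or the indications it covers. Anyone searching for it finds 50 IU/kg everywhere except in one sentence about a different indication, which reaches 60 IU/kg. The ceiling stands in the paragraph on bleeds, so it is fair to ask whether a surgery dose should set it.

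The surgery range also looks odd on its own. By the protocol's conversion it produces a higher peak than the range for life-threatening bleeds, and its digits match a Table 5-1 row expressed in IU/dl.

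Conduct is what would be at stake. Bleeds may be treated at home with doses set beforehand. If sites and monitors held different ceilings, the same bleed injection between 50 and 60 IU/kg could be recorded as a deviation at one site and accepted at another.

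**Working it through.** **Inputs**, all from section 5.3 unless stated: prophylaxis 20-50 IU/kg; Table 5-1 levels 20-40, 30-60 and 60-100 IU/dl; minor surgery 30-60 IU/kg; dose (IU/kg) = 0.5 × level (IU/dl), or equivalently level = 2 × dose; vial size 2000 IU (Table 9-1); treatment for 8 weeks, or 56 days.

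**Protocol's own examples.** 50 kg × 40 IU/dl × 0.5 = 1000 IU, as printed. 2000 IU / 70 kg × 2 = 57.1 IU/dl, printed as 57. Both reproduce.

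**Every range on both scales.**

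| Use | IU/kg per injection | IU/dl |
|---|---|---|
| Early bleed | 10-20 (derived) | 20-40 |
| More extensive bleed | 15-30 (derived) | 30-60 |
| Life-threatening bleed | 30-50 (derived) | 60-100 |
| Prophylaxis | 20-50 | 40-100 (derived) |
| Minor surgery | 30-60 | 60-120 (derived) |

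The maximum over all rows is 60 IU/kg; without surgery it is 50 IU/kg. The gap is 10 IU/kg (10/50 = 20%).

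**Could the cap be an absolute dose in IU?** The largest absolute dose printed is 2000 IU, in the 70 kg example. For that patient the permitted prophylaxis dose runs up to 50 × 70 = 3500 IU, so a 2000 IU cap would forbid doses that section 5.3 allows. The cap therefore only makes sense per kilogram.

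**Size of the difference per injection.** At 70 kg: 60 × 70 = 4200 IU (2.1 vials) against 3500 IU (1.75 vials). At 50 kg: 3000 IU against 2500 IU.

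**When it matters.** A bleed dose above 50 IU/kg means a target above 50 × 2 = 100 IU/dl, beyond the highest row of Table 5-1.

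**Effect on the consumption endpoint** (section 17.4.1.1, summarised descriptively). Planned prophylaxis over 8 weeks runs from 24 × 20 = 480 IU/kg (3 times weekly) to 28 × 50 = 1400 IU/kg (every second day). One injection at 60 instead of 50 IU/kg adds 10/1400 = 0.7% to 10/480 = 2.1% for that patient, or 10 × 365/56 = 65 IU/kg/year annualised.

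**Is the surgery range inconsistent with Table 5-1?** Its upper end is 120 - 100 = 20 IU/dl above the life-threatening row for a single injection. Per 24 hours, surgery is 1 × 30-60 = 30-60 IU/kg, while the life-threatening row spans 1 × 30 = 30 to 3 × 50 = 150 IU/kg. The daily surgery amount lies inside that span. The quantities also differ in kind: Table 5-1 gives levels to be maintained until the bleed resolves, whereas 120 IU/dl is the predicted rise after one dose.

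**The case for a change.** The best case for a change runs as follows. Once the guidance is declared advisory, the cap is the one dosing limit that section 5.3 states in its own words, so it should carry a number. It refers to this protocol, so the label cannot supply the figure. Two careful readers can reach 60 and 50 IU/kg, and section 19.1 requires deviations to be documented, so the classification matters. Section 8.4.5 describes minor surgery as superficial, which makes a peak above the life-threatening row hard to understand, and the matching digits invite a check of the unit. The remedy would be one sentence.

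Part of this stands: number, unit and scope are not printed, and a site could adopt the narrower reading. The rest is weaker.

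- The cap sentence names the whole protocol, not bleeds or Table 5-1. The 50 IU/kg reading must exclude surgery doses without saying so, and must borrow a prophylaxis figure or a conversion, since no bleed dose of 50 IU/kg is printed.
- A ceiling above the guide values does not conflict with them, because section 5.3 allows departures from the guide.
- Bleed dosing is also tied to the approved prescribing information, so the cap is not shown to be the sole restraint.
- The minor-surgery row of Table 8-6 also covers vascular cut-down, implanted pumps and venous access devices, biopsies, and catheters entering a body cavity by needle or guide wire. The range is less out of place than the first half of that definition suggests.
- Matching digits do not show a unit error. Only the prescribing information could settle that, and it is not among the documents. Whether minor surgery warrants a given peak level is a clinical judgement.
- Accidental wrong doses are judged against the intended dose (section 12.1.4), so error reporting does not depend on this cap.

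**Conclusion.** No change to the plan follows. As worded, section 5.3 yields a usable per-injection ceiling of 60 IU/kg; leaving surgery out would give 50 IU/kg. The whole issue is that 10 IU/kg band, and it is entered only if an investigator aims for a bleed level above 100 IU/dl. The primary inhibitor endpoint and the sample size make no use of the cap, and no formal testing is planned. Consumption would shift by 0.7% to 2.1% of one patient's planned 8-week prophylaxis per such injection.

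This rests on two assumptions: that the cap is meant per kilogram, which the protocol's own prophylaxis range supports, and that injections in the band are few, which follows from their lying above the highest guide row but cannot be counted in advance. The surgery range and Table 5-1 differ by indication; the documents show neither a contradiction nor a unit slip. If a site asks, the sponsor's clinical team can state the ceiling and its scope in routine site guidance. That supplies a detail and alters no analysis, and the clinical figures remain theirs to decide.
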